5.2 Data Source

Truven MarketScan Claims Database (01JUL2013-30JUN2018)

MarketScan offers the largest proprietary claims-based convenience sample available, with 69 million unique patients since 1996. In the most recent data year, the databases contain data on 29 million covered lives. The stability of MarketScan data sources allows superior continuity of patients over multiple years, which is generally longer than other claims databases. This is due to the fact that the majority of the data is sourced from large employers. Employer-provided data also allow tracking of patients across health plans. This tracking ability is useful because people change health plans more often than they change jobs, and these data are able to capture patients who are “lost” in plan-based data sources—upward of 17% of patients in those databases. In the most recent 5 years of MarketScan data, nearly 29 million patients (73%) have at least 12 months of continuous enrollment.

The MarketScan claims databases contain complete information on outpatient prescriptions. These databases afford distinct advantages over others that track only prescription fills, as the data allow for disease type identification (from medical claims) and can be used to determine whether clinical, demographic, and provider characteristics influence prescribing patterns. Because individual patients’ prescription fills are recorded, therapies prescribed concurrently (and presumably used in combination) can also be identified. This provides vital information about actual drug use patterns, as opposed to individual drug prescription trends.

[2019-8636] Observational Study Protocol

VHA Database (01APR2013-31MAR2018)

The VHA is the largest integrated health care system in the US, providing quality care at efficient prices for >9 million veterans across the country. According to VA estimates, there were about 22 million living US veterans in 2014.²³

The size and structure of the VHA system differs from most private care organizations. The system includes:

- 153 medical centers;
- 136 nursing homes;
- 207 Vet Centers;
- 882 ambulatory care and community-based outpatient clinics;
- 45 residential rehabilitation treatment programs;
- 92 comprehensive home-based care programs;
- 13,000 physicians;
- nearly 55,000 nurses; and
- >9 million enrollees^{24,25}

[2019-8636] Observational Study Protocol

Figure 4 VHA Data Elements

VHA Database					

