- had ≥ 2 claim with an ICD-9/10-CM code (Appendix 1) for T2DM in any position (primary/secondary) at any time prior to the index date;
- were aged ≥ 18 years on the index date;
- had continuous health plan enrollment with medical and pharmacy benefits for ≥ 9 months pre- and post-index event;
- had ≥ 1 prescription claim for any insulin other than U-500R (Table 1) in the pre-index period;
- had ≥ 1 HbA1c measurement within 90 days pre-index or 30 days post-index event;
- had ≥ 1 HbA1c measurement after the 30-day post-index period at any time in the follow-up period;
- had claims indicating TDD >180 in the post-index period;

[2019-8636] Observational Study Protocol

- had claims indicating TDD >180 in the pre-index period; and

Exclusion Criteria

Patient will be excluded if they:

- had both T1DM and T2DM, had no OADs (Appendix 1) other than metformin, with the ratio between the number of T1DM and T2DM claims >0.5 at any time in the study period (VHA: 01APR2013–31MAR2018; Truven: 01JUL2013–30JUN2018);
- had previous use of U-500R in the 9-month pre-index period;
- had ≥ 1 claim with a ICD-9/10-CM code (Appendix 1) for secondary diabetes, gestational diabetes, diabetes complicating pregnancy, childbirth, puerperium, or non-clinical diabetes at any time during the pre-index period;
- had evidence of pump use (Appendix 2) in the post-index period;
- had claims indicating TDD above 2000 units/day at any time in the pre-index or post-index periods; or
- had claims indicating insulin use other than U-500R in the post-index period.

Sample selection criteria for any U-500R Initiators [Index Event c]Inclusion Criteria

Patient will be included if they:

- had ≥ 1 prescription claim for U-500R syringe or Kwikpen administration during the identification period (VHA: 01JAN2014–30JUN2017; Truven: 01JUL2014–30JUN2017), with the first prescription claim for U-500R syringe or Kwikpen administration designated as Index Event c, and the date designated as the index date;
- had ≥ 2 claim with an ICD-9/10-CM code (Appendix 1) for T2DM in any position (primary/secondary) at any time prior to the index date;
- were aged ≥ 18 years on the index date;
- had continuous health plan enrollment with medical and pharmacy benefits for ≥ 9 months pre- and post-index event;
- had ≥ 1 prescription claim for any insulin other than U-500R (Table 1) in the pre-index period ;
- had ≥ 1 HbA1c measurement within 90 days pre-index or 30 days post-index event;

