- had ≥ 1 HbA1c measurement after the 30-day post-index period at any time in the follow-up period;
- had claims indicating TDD >180 in the post-index period; and
- had claims indicating TDD >180 in the pre-index period

[2019-8636] Observational Study ProtocolExclusion Criteria

Patient will be excluded if they:

- had both T1DM and T2DM, had no OADs (Appendix 1) other than metformin, with the ratio between the number of T1DM and T2DM claims >0.5 at any time in the study period (VHA: 01APR2013–31MAR2018; Truven: 01JUL2013–30JUN2018);
- had previous use of U-500R in the 9-month pre-index period;
- had ≥ 1 claim with a ICD-9/10-CM code (Appendix 1) for secondary diabetes, gestational diabetes, diabetes complicating pregnancy, childbirth, or puerperium, or non-clinical diabetes at any time during the pre-index period;
- had evidence of pump use (Appendix 2) in the follow-up period;
- had claims indicating TDD above 2000 units/day at any time in the pre-index or post-index periods; or
- had claims indicating insulin use other than U-500R in the post-index period.

Note:

- All high-dose U-500R patients will be defined by having an average TDD of >180 units per day, with no additional insulin used concomitantly or no U-500R pump use.
- Since the Truven claims database does not include lab data, the ≥ 1 HbA1c criterion will be removed from the selection criteria while using this database.
- For analysis conducted using the Truven claims database, the pre-index period and the post-index period will be 12 months instead of 9 months.
- The corresponding ICD-9/10 codes for all the diagnoses and the NDC codes for the insulin treatments are provided in Appendix 1.

Subgroup analysis:

- Elderly (≥ 65 years) patients among each of the high-dose U-500R Kwikpen, high-dose U-500R syringe, and any high-dose U-500R initiator cohorts will be flagged, and a subgroup analysis will be performed comparing the treatment patterns and outcomes (HbA1c and hypoglycemia) before and after U-500R initiation.
- Patients with a TDD of 201-300 units in the post-index period among each of the high-dose U-500R Kwikpen, high-dose U-500R syringe, and any high-dose U-500R initiator cohorts will be flagged, and a subgroup analysis will be performed comparing the treatment patterns and outcomes (HbA1c and hypoglycemia) before and after U-500R initiation.

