5.5 Variables/Measures

Table 2 presents the study variables and operational definitions.

Table 2 Variables and Definitions

Variable	Source	Definition
Exposure		
Insulin use	Truven: Outpatient pharmacy claims table VHA: Pharmacy file	Index Event a : any insulin use other than U-500R in the pre-index and high-dose U-500R syringe use in the post-index period Index Event b : any insulin use other than U-500R in the pre-index and high-dose U-500R Kwikpen use in the post-index period Index Event c : any insulin use other than U-500R in the pre-index and high-dose U-500R Kwikpen/syringe use in the post-index period
Patient Characteristics*		

[2019-8636] Observational Study Protocol

Variable	Source	Definition
Age	Truven: Inpatient service table, outpatient service table, outpatient pharmacy claims table VHA: Enrollment file	Age will be retained in the dataset as a continuous variable for groups aged 18-25, 26-35, 36-45, 46-55, 56-64, and ≥ 65 years.
Sex	Truven: Inpatient service table, outpatient service table, outpatient pharmacy claims table VHA: Enrollment file	A flag will be created for male and female patients.
Race (only VHA)	VHA: Enrollment file	A flag will be created for white, black, and other race patients.
US Region (only Truven)	Truven: Inpatient service table, outpatient service table, outpatient pharmacy claims table	A flag will be created for patients residing in the Northeast, Northcentral, South, and West US regions.
Medicare eligibility (only Truven)	From Truven	A flag will be created for patients who are enrolled in Truven Medicare.
Body mass index (BMI)	VHA: Vital Status file	BMI on the index date will be calculated and reported as a continuous variable.
Quan-Charlson comorbidity index (CCI) score ²⁶	Truven: Inpatient service table, outpatient service table VHA: Inpatient and outpatient files	Quan-CCI score will be constructed using enhanced ICD-9/10-CM codes for 17 different comorbid conditions.
Individual Comorbidities ²⁷	Truven: Inpatient service table, outpatient service table VHA: Inpatient and outpatient files	A flag will be created using ICD-9/10-CM codes (Appendix 1) for patients diagnosed in the pre-index period with any of the following individual comorbidities: retinopathy, nephropathy, neuropathy, coronary artery disease, peripheral vascular disease, congestive heart failure, hypertension, depression, obesity, or malignant tumor.
Health Economics Outcomes Research (HEOR) Outcomes		

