Out-of-pocket pharmacy costs will be analyzed descriptively before and after high-dose U-500R syringe initiation, high-dose U-500R Kwikpen initiation, and any high-dose U-500R initiation. Numbers and percentages will be provided for dichotomous and polychotomous variables. Means and SDs, along with the median, minimum and maximum will be provided for continuous variables. To determine the statistical significance of before and after values, McNemar's test will be used for categorical variables, and the paired t-test will be used for continuous variables.

Multivariate Analysis

A generalized linear mixed model (details above) with log link will be used to evaluate factors associated with insulin-related out-of-pocket pharmacy costs in the pre-and post-index periods among high-dose U-500R syringe initiators, high-dose U-500R Kwikpen initiators, and any high-dose U-500R initiation. For this objective, the mixed linear model will help to evaluate the effect of both time-varying and time-independent variables on the costs, while taking into account for correlation due to multiple assessments from the same individual. In the current model, costs (measured at 2 time intervals [before and after the index event; U-500R initiation]) will be designated as the dependent variable. Observed TDD will be designated as the time-varying covariate in the model (measured both before and after the index date), and the time-independent covariates will include the demographic and clinical characteristics.

The complete list of covariates will include:

- age;
- sex;
- region;
- pre-index CCI score;
- observed TDD from claims ;
- Medicare (yes/no); and
- time (pre/post).

[2019-8636] Observational Study Protocol

[figure not shown]
Note:

- ❖ Age, sex, region, Medicare (yes/no), and CCI score will be assessed during the pre-index period. Observed TDD will be calculated during both the entire pre-index and post-index periods.
- ❖ Adherence will not be included as a covariate here due to the high collinearity between time and adherence.

Exploratory Analysis: Mediator Effect of Adherence (PDC) and Observed Total Daily Dose (TDD) on Insulin-related Pharmacy Costs

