Mediation analysis following the below modeling steps will be considered to understand the impact of index event (time: pre-index indicates use of other non-U-500R insulins and post-index indicates exposure to U-500R use) on insulin-related out-of-pocket costs through potential mediators. Adherence (measured by PDC) and Observed Total Daily Dose (TDD) are considered as potential mediators between costs and treatment period (i.e. exposure). The key steps in mediation analysis include a model of the outcome (costs) as a function of both the mediators (PDC, and TDD) and the predictor (treatment period) and a model of the mediators (PDC and TDD) as functions of the predictor (treatment period). Confounders will be included in the models. Unfortunately, certain confounding variables are unobserved in claims data, e.g., weight, HbA1c.

- 1.) Suppose the dataset consists of n patients. For patient i ($i = 1, \dots, n$), denote by Y_{ik} the outcome variable of interest, e.g. costs, during the period k ($k = 0, 1$), where $k = 0$ refers to pre-index period and $k = 1$ refers to the post-index period.
- 2.) Let M_{ijk} be the mediators at period k , and $j=1,2$ denotes the different mediators PDC and TDD
- 3.) Let A_{ik} be a binary indicator of treatment during period k . Write $\mathbf{A}_i = \{A_{ik}\}_k$. According to the design, all the patients did not take the U-500R during the pre-index period, but they took the U-500R during the post-index period, thus $A_{ik} = k$ for $k = 0, 1$.
- 4.) A set of covariates as potential confounding variables, including age, sex, region, pre-index CCI score.

$$Y_{ik} = \beta_0 + \beta_A A_{ik} + \beta_{M1} M_{i1k} + \beta_1 \text{Age} + \beta_2 \text{Sex} + \beta_3 \text{Region} + \beta_4 \text{CCI} + \beta_5 M_{i1k} + \beta_6 M_{i2k} + d_i + \varepsilon_{ik}$$

$$M_{ijk} = \alpha_0 + \alpha_{Aj} A_{ik} + \alpha_{1j} \text{Age} + \alpha_{2j} \text{Sex} + \alpha_{3j} \text{Region} + \alpha_{4j} \text{CCI} + b_{0i} + b_{Mij} + b_{Ai} A_{ik} + \eta_{ijk},$$

where random errors ε_{ik} and η_{ijk} along with random effects d_i , b_{0i} and b_{Ai} are mutually independent over i, j, k . The random effects b_{i0} and b_{iA} capture the dependence among M_{ijk} 's. The random effects d_i 's, control the dependence between the outcome variable between the pre-index and post-index periods given the mediators and confounders,

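### Medicare status in the Truven cost analysis is fixed at its pre-index value, so any change between commercial and Medicare coverage across the two windows would load on the pre/post term

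*Protocol*

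**What the plan says.** Protocol section 6.4.1, Exploratory Objective 3, specifies a log-link generalized linear mixed model for insulin-related out-of-pocket pharmacy costs, with two records per patient. Its covariates are age, sex, region, pre-index CCI, observed TDD, Medicare (yes/no) and time (pre/post). The note under the list states: "Age, sex, region, Medicare (yes/no), and CCI score will be assessed during the pre-index period". One covariate is allowed to change: "Observed TDD will be designated as the time-varying covariate in the model (measured both before and after the index date").

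The mediation analysis in the same section defines the exposure as the period: "pre-index indicates use of other non-U-500R insulins and post-index indicates exposure to U-500R use". Its confounders are introduced as "A set of covariates as potential confounding variables, including age, sex, region, pre-index CCI score". Neither written equation has a Medicare term. The descriptive comparison is a paired t-test with no payer adjustment.

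On who can be in the sample:

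- Section 5.5 (Table 2) defines the payer variable without a date: "A flag will be created for patients who are enrolled in Truven Medicare".
- Section 5.3.1 requires that patients "had continuous health plan enrollment with medical and pharmacy benefits for ≥ 9 months pre- and post-index event", and its notes add: "For analysis conducted using the Truven claims database, the pre-index period and the post-index period will be 12 months instead of 9 months".
- Section 5.2 says of the source: "Employer-provided data also allow tracking of patients across health plans".

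**The concern.** The analysis is a within-patient comparison. A covariate with one value per patient explains differences between patients and cannot explain a change within one. Besides observed TDD, the only model term that differs between a patient's two records is time (pre/post), which the protocol equates with U-500R exposure. If a patient's payer changes between the windows, the change in what that patient pays has nowhere else to go.

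Payer rules are central to the cost question. Section 3 builds the cost hypothesis on copays per refill. Sections 3 and 5.1 lengthen the Truven windows so that deductibles are captured. Section 6.4.1 interprets the mediation direct effect as the change in copay that comes with moving to U-500R. A change of payer can alter copays and deductibles without any effect of the drug. At stake is whether part of a reported saving or extra cost under U-500R reflects a change of payer.

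**Working it through.** The protocol gives no figure to reproduce: it reports no payer mix, no coverage changes and no cost-sharing levels, and its preliminary counts (Table 3) are for VHA only. The check therefore asks whether the written model lets a payer change through, and how large the effect would be over a stated range of assumptions.

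**Inputs from the protocol.** Two 12-month windows; Medicare fixed pre-index; TDD the named time-varying covariate; period equal to exposure; no same-payer requirement.

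**Assumptions, not in the protocol.**
- s = share of patients moving from commercial to Medicare coverage within the 24 months: 2%, 5%, 10%.
- r = mean out-of-pocket cost under Medicare relative to commercial: 0.5 to 2.
- Switch dates uniform over the 24 months.
- True U-500R effect on cost: none (ratio 1.00).

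**Step 1, time on Medicare among switchers.** Half switch before index: on average they spend half of the pre-index window and all of the post-index window on Medicare. Half switch after index: none of the pre-index window and, on average, half of the post-index window. Mean share before = 0.5 × 0.5 = 0.25. Mean share after = 0.5 × 1 + 0.5 × 0.5 = 0.75. Across the cohort, the Medicare share of time rises by s/2.

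**Step 2, spurious cost ratio with non-switchers at commercial cost.**

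Ratio = [1 + 0.75 s (r − 1)] / [1 + 0.25 s (r − 1)]

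| s | r = 0.5 | r = 2 |
|---|---|---|
| 2% | 0.9925 / 0.9975 = 0.995 | 1.015 / 1.005 = 1.010 |
| 5% | 0.98125 / 0.99375 = 0.987 | 1.0375 / 1.0125 = 1.025 |
| 10% | 0.9625 / 0.9875 = 0.975 | 1.075 / 1.025 = 1.049 |

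**Step 3, patients already on Medicare.** If a share p is on Medicare throughout, 0.75 s becomes p + 0.75 s and 0.25 s becomes p + 0.25 s. With p = 0.5 and s = 10%: at r = 0.5, 0.7125 / 0.7375 = 0.966; at r = 2, 1.575 / 1.525 = 1.033. The limits move, but the order of magnitude does not.

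**Step 4, switchers only (s = 1, p = 0).** At r = 0.5, 0.625 / 0.875 = 0.714, about −29%. At r = 2, 1.75 / 1.25 = 1.40, or +40%.

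**Step 5, does the frozen flag remove it?** A simulation used a log-link gamma model without random effects, 100,000 patients per scenario, 40% already on Medicare, and a true ratio of 1.00. Estimated time ratios at s = 10%:

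| r | Medicare omitted | Frozen at pre-index | Per window |
|---|---|---|---|
| 0.5 | 0.968 | 0.974 | 1.000 |
| 2 | 1.040 | 1.051 | 1.004 |

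Over all nine scenarios (r = 0.5, 1.5, 2), the frozen flag gave 0.974 to 1.051 and the per-window flag 0.997 to 1.004. Freezing the flag does about as little as leaving it out.

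One smaller run (3,000 patients, s = 10%, r = 0.5) fitted a linear mixed model to log cost. It gave 0.933 with Medicare omitted, 0.933 frozen and 0.969 per window. With two records per patient, a constant covariate leaves the time estimate unchanged, so the first two figures agree. A run of that size is noisy, so its distance from 1.00 should not be over-read; the larger runs are the better guide to recovery.

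**The case against.** The strongest reply is that the protocol never shows that such patients exist. The remark about tracking people across plans concerns people changing health plans while staying with an employer; it does not say that anyone is followed from commercial coverage into Medicare. Continuous health plan enrolment could be read as one unchanged plan, which would remove switchers. Every number in the calculation is assumed. Measuring covariates before index is the plan's uniform convention. Other plan or formulary changes would load on time in the same way. The objective is exploratory, and the regression is described as looking for associated factors.

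Much of this stands. A reader might infer that patients reaching 65 are known to move into Medicare within the sample, that movement is one way, and that the cost change is therefore being credited to U-500R. The documents support none of that as fact: they give no count of switchers, no direction and no cost ratio. Nor should a change of −50% to +100% among switchers be taken as typical, since it requires a switch exactly at index. A cohort-wide figure that treats everyone else as commercially insured also depends on that denominator, as Step 3 shows.

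The mediation list is introduced as open-ended, so a separate analysis plan could add Medicare; only its absence from the written equations can be stated.

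What the reply does not remove is the structure. The enrolment criterion does not require the same payer, no rule excludes or re-flags patients whose coverage changes, and the protocol itself judged Medicare relevant enough to adjust for, but fixed it in a form that cannot act on the within-patient comparison.

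**Conclusion.** The point holds as a conditional one. If coverage changes between commercial and Medicare across the two windows, the written cost model and mediation equations would attribute the resulting cost change to the pre/post term and the direct effect. Size and sign are unknown from the protocol. Under the assumed 2% to 10% of switchers and cost ratio of 0.5 to 2, with non-switchers at commercial cost, the spurious post/pre ratio is about 0.97 to 1.05. It would be 1.00 if nobody switches. This is a modest weakness in an exploratory objective and touches only the Truven cost results; treatment patterns, HbA1c and hypoglycaemia are unaffected. It is worth correcting because the correction is cheap, not because a material bias has been shown.

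**What to change.** Derive the Medicare flag, or the share of the window spent on Medicare, separately for the pre-index and post-index periods. Enter it as a time-varying covariate in the cost model and add it to the mediation equations for both costs and mediators. Amend the note in section 6.4.1 and the Table 2 definition to match. Report the paired comparison of costs also in patients whose payer type is the same throughout both windows, and state how many changed.

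The cost is minor programming on a variable already planned, a wording change, and a somewhat smaller sample in the sensitivity analysis (2% to 10% fewer patients under the assumed range). Adjusting for a variable measured after index needs a reason; here, starting U-500R is unlikely to affect which payer a patient has.

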[2019-8636] Observational Study Protocol

Variable	Source	Definition
Observed TDD in claims	Truven: Outpatient pharmacy claims table VHA: Pharmacy file	
The observed insulin TDD will be calculated as the total number of insulin units/total unique days of supply as recorded in claims and will be calculated both in the pre-and post-index periods among the high-dose U-500R Kwikpen initiators, high-dose U-500R syringe initiators, and any high-dose U-500R initiators. TDD will be reported as both a continuous and categorical variable.
 
For high-dose U-500R syringe initiators (Index Event a):
 
Total insulin units correspond to all the insulin units in pre-index and post-index periods, respectively.
 
For high-dose U-500R Kwikpen initiators (Index Event b):
 
Total insulin units correspond to all the insulin units in pre-index and post-index periods, respectively.
 
For any high-dose U-500R initiators (Index Event c):
 
Total insulin units correspond to all the insulin units in pre-index and post-index periods, respectively.
 
Note:
 
For the unique days supply in patients with evidence of a basal-bolus regimen, or basal/bolus-pre-mixed or basal/bolus-U-500R, the overlap days will be adjusted for the concomitant use of basal and bolus insulin products, but will not be adjusted within basal and within bolus insulins.

Change in observed TDD		The change in observed TDD will be defined as the difference between the pre- and post-index observed TDD.

[2019-8636] Observational Study Protocol

Variable	Source	Definition
Observed average daily dose (ADD) in claims	Truven: Outpatient pharmacy claims table VHA: Pharmacy file	
The observed insulin ADD will be calculated both in the pre-and post-index periods among the high-dose U-500R Kwikpen initiators, high-dose U-500R syringe initiators, and any high-dose U-500R initiators. ADD will be reported as both a continuous and categorical variable.
 
Pre-index ADD: the total number of insulin units/the total number of days in the pre-index period.
 
Post-index ADD: the total number of insulin units/ the total number of days in the post-index period
 
Note: Total insulin units calculation in based on the similar approach as described in TDD.

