Adherence	Truven: Outpatient pharmacy claims table VHA: Pharmacy file	
Adherence to insulin will be assessed using the proportion of days covered (PDC), and reported in categories of 0-20%, 20-40%, 40-60%, 60-80%, and 80%-100%. PDC will be calculated both in the pre-and post-index periods among the U-500R Kwikpen initiators, U-500R syringe initiators, and any U-500R initiators.
 
For high-dose U-500R syringe initiators (Index Event a): PDC before U-500R initiation will be calculated as the number of days covered by the prescription claims of insulin (any insulin)/total days in the pre-index period. PDC after U-500R initiation will be calculated as the number of days covered by the prescription claims of insulin /total days in the post-index period.
 
For high-dose U-500R Kwikpen initiators (Index Event b):

[2019-8636] Observational Study Protocol

Variable	Source	Definition
		
PDC before U-500R initiation will be calculated as the number of days covered by the prescription claims of insulin (any insulin)/total days in the pre-index period.
 
PDC after U-500R initiation will be calculated as the number of days covered by the prescription claims of insulin /total days in the post-index period.
 
For any high-dose U-500R initiators (Index Event c):
 
PDC before U-500R initiation will be calculated as the number of days covered by the prescription claims of insulin (any insulin)/total days in the pre-index period.
 
PDC after U-500R initiation will be calculated as the number of days covered by the prescription claims of insulin /total days in the post-index period.
 
Note: For the calculation of PDC in patients with evidence of a basal-bolus regimen, basal/bolus-premixed, or basal/bolus-U-500R, the overlap days will be adjusted for the concomitant use of basal and bolus insulins, but will not be adjusted within basal and within bolus insulins.

Abandonment/fill rates	Truven: Outpatient pharmacy claims table VHA: Pharmacy file	The average number of insulin prescription fills will be calculated in the follow-up period among all the study cohorts.
Claim gaps	Truven: Outpatient pharmacy claims table VHA: Pharmacy file	The average gap between prescription fills of insulins will be calculated in the pre- and post-index periods among all the study cohorts.

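### The cost mediation treats PDC and TDD as separate mediators although they share recorded supply days with opposite effect, and the mediator model cannot represent the negative correlation that results

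*Protocol*

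**What the plan says.** Section 6.4.1 decomposes the change in insulin-related out-of-pocket cost into a direct effect of the switch (the change in copay) and indirect effects: "Adherence (measured by PDC) and Observed Total Daily Dose (TDD) are considered as potential mediators between costs and treatment period (i.e. exposure"). The cost equation contains period, PDC and TDD additively. Each mediator has its own period effect, and neither appears in the other's equation. Residuals are declared independent over patient, mediator and period, and dependence between mediators is left to patient-level random effects common to both equations. Intervals come from a parametric bootstrap.

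Table 2 (Section 5.5) defines the variables:
- TDD is "the total number of insulin units/total unique days of supply as recorded in claims".
- PDC before the switch is "the number of days covered by the prescription claims of insulin (any insulin)/total days in the pre-index period"; after it, "PDC after U-500R initiation will be calculated as the number of days covered by the prescription claims of insulin /total days in the post-index period".
- ADD is "the total number of insulin units/the total number of days in the pre-index period", and likewise after the switch.
- For basal-bolus and similar combined regimens, the TDD note says that "the overlap days will be adjusted for the concomitant use of basal and bolus insulin products, but will not be adjusted within basal" or within bolus insulins. PDC carries the same rule.

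The mediation text takes TDD to express the quantity of insulin obtained and PDC to express the number of days with insulin.

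**The concern.** The two mediators are built from one count of supply days, used in opposite ways. If that count moves at the switch for a reason other than use, PDC and TDD change in opposite directions although the patient bought the same insulin and paid the same. The decomposition would then show an adherence path and an opposing dose path, and possibly a copay effect, none of them real.

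Such a movement is plausible. Section 3 expects basal-bolus regimens before the switch, where the overlap adjustment applies. Section 5.3.1 excludes any other insulin after it, so the adjustment has nothing to act on. The supply-day rule therefore works differently on the two sides of the exposure.

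Two further points follow. Quantity obtained is not expressed by TDD alone; by Table 2 it is PDC x TDD. And shared supply days push the two mediators towards negative correlation, which the stated error structure cannot hold. The only limitation that the mediation section gives is unobserved confounding, such as weight and HbA1c.

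**Working it through.** The plan states no figure on this point, so there is none to reproduce.

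**1. Identity (Table 2).** Let U be units, S unique supply days and D days in the period. PDC x TDD = (S/D) x (U/S) = U/D = ADD. It is exact when the supply days in TDD equal the covered days in PDC; Table 2 does not say how supply past the window end is treated.

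Illustration with D = 365, U = 73,000:

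| S | PDC | TDD | ADD |
|---|---|---|---|
| 292 | 0.80 | 250 | 200 |
| 292 x 0.8 = 233.6 | 0.64 | 312.5 | 200 |
| 292 x 1.25 = 365 | 1.00 | 200 | 200 |

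**2. Effect of a supply-day shift alone.** Assumptions, not from the documents: fills F and units per fill q each have log-SD 0.2, supply days per fill s have log-SD 0.1 to 0.2, and all are independent. The cost equation is read with each mediator once (as printed, the PDC term appears twice). On the log scale PDC is F + s and TDD is q - s. Write a, b, c for the variances of F, q, s.

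- *Cost proportional to units:* log cost = F + q, so both coefficients are 1.
- *Copay per fill* (the mechanism in Section 3 and in the mediation text): log cost = F. The PDC coefficient is a(b+c)/(ab+ac+bc) and the TDD coefficient is ac/(ab+ac+bc). With a = b = 0.04, c = 0.01 gives 0.833 and 0.167; c = 0.04 gives 0.667 and 0.333.

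For 15% fewer recorded days, ln 0.85 = -0.163:

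| Mechanism | PDC path | TDD path | Direct |
|---|---|---|---|
| Units | -0.163 | +0.163 | 0 |
| Copay, c = 0.01 | -0.135 | +0.027 | +0.108 |
| Copay, c = 0.04 | -0.108 | +0.054 | +0.054 |

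The true value of every entry is 0. Simulations of the planned linear random-intercept model agree: about -15% and +16% of cost if cost tracks units, and -9% to -15% and +1% to +5% under a copay per fill. A separate set with supply days multiplied by 0.8, 1,000 patients and mean cost of about 507 to 551 gave these results (one supply-day noise setting shown):
- Unit-proportional cost: -110.5 (PDC), +106.5 (TDD), direct +1.5.
- Cost half dependent on dose: -94.4, +58.4, direct +34.5.
- Copay per fill: -80.7, +17.7, direct +62.9.

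With no shift, all effects were about 0.

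**3. Error structure.** The period effects on PDC and TDD are estimated from within-patient changes. In the stated model the covariance of those two changes is the variance of the shared random slope b_Ai, because the random intercepts cancel; it cannot be negative. Shared supply days give correlation -c/sqrt((a+c)(b+c)), which is -0.2 at c = 0.01 and -0.5 at c = 0.04. The closest that the model can come is zero.

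Ratio of assumed to true SE of the joint indirect effect (mediator-model part only), for coefficients B1, B2: sqrt[(B1²(a+c) + B2²(b+c)) / (B1²(a+c) + B2²(b+c) - 2·B1·B2·c)].
- Unit-proportional: sqrt(0.10/0.08) = 1.12 to sqrt(0.16/0.08) = 1.41.
- Copay per fill: sqrt(0.0361/0.0333) = 1.04 to sqrt(0.0444/0.0267) = 1.29.

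Wider sets of assumed SDs gave correlations of -0.1 to -0.6 and an SE about 1% to 60% too large.

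**4. ADD as the only mediator.** Take a copay per fill, fills and payments unchanged, and observed dose truly up 40% (assumed). The slope of log cost on log ADD is a/(a+b) = 0.5. The false indirect effect is 0.5 x ln 1.4 = +0.168 and the direct effect takes the opposite sign; simulation gave about -16%. The planned model gave about -2% to -10%.

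**The case against.** The case for leaving the plan alone has four parts.

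- *Fills and dose per day are distinct.* A product identity does not make two variables redundant. This stands: both coefficients can be estimated, and without a supply-day shift the paths come out right. A reader might infer that the separate paths are not identified, but the definitions do not show that. The problem is measurement error in days' supply that differs between periods.
- *No shift is documented.* This stands. The only before-and-after data cited (Section 3, Kwikpen initiators) report dose and PDC both rising, which is not the pattern of a pure supply-day artefact. It does not exclude a partial one.
- *The interval error is conservative and may be small.* This stands in part: the interval is too wide, not too narrow, when both cost coefficients are positive, and under a copay with little supply-day variation the excess is a few percent. The appeal to the shared random effects does not rescue the structure, since they cannot produce a negative covariance.
- *The analysis is exploratory, is only to be considered, and does not commit to reporting each path.* True. But Section 4.1 asks for the mediator effect of adherence and observed TDD, and the section claims a causal interpretation, so a split is likely to be read into the results.

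A reader might also conclude that ADD should be the sole mediator because it is free of supply days. Step 4 shows why not: under the protocol's own copay mechanism, a real dose increase would then appear as a copay saving, the direction that Section 3 hypothesizes.

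**Conclusion.** The point holds in a limited form. PDC and TDD share recorded supply days with opposite effect, and quantity obtained is their product, not TDD. A supply-day change unrelated to use would create false opposing paths. A false direct effect is not automatic: it is about zero if cost is proportional to units and appears when cost depends on dose less than proportionally, as with a copay per fill. For an assumed 15% drop in supply days, the false PDC path is roughly 9% to 15% of cost, and the false TDD path runs from 1% to 5% under a copay to about 16% if cost tracks units. Independently of any shift, the mediator model cannot represent the negative correlation that shared supply-day variation induces, so with positive cost coefficients the interval for the joint indirect effect is too wide, by an amount that depends on that variation and on the cost mechanism.

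The size of the shift, the log-SDs and the cost mechanisms are assumptions. The consequence is bounded because the objective is exploratory.

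**What to change.** In the mediation model of Section 6.4.1:

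1. Let the within-period PDC and TDD errors have an unstructured covariance that can take either sign, and run the parametric bootstrap from that model.
2. Report the joint indirect effect of PDC and TDD as the mediation result, and give the separate changes in PDC and TDD descriptively.
3. State that any split between the two paths, and the direct effect, are sensitive to changes in recorded days' supply. Joint reporting and correlated errors do not remove a false direct effect. Correct the statement that quantity is expressed by TDD.
4. Optionally add a model with ADD as mediator as a sensitivity analysis that does not depend on supply days, with the caveat that under a copay per fill it shows a false saving when dose rises. It should not replace the planned model.

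The cost is a change of wording and one covariance parameter; ADD is already computed. The loss is that no separate adherence and dose contributions to cost are claimed.
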